Participants will then be invited to a debriefing interview to provide us feedback on the ITI, including the module. Feedback interviews will be conducted by a (master-level) RA and will be audio-recorded. Please see Appendix 8 for sample patient feedback interview guide; provided are guides in English, once finalized guides will be translated in Arabic.

Participants will receive compensation of 700 EGP per session, for a total of three sessions (two ITI sessions and one feedback session).

Therapeutic program

The first three modules will be provided in a group, face-to-face setting in either AUC campus or other clinics (see Section 3.7). Due to clinical reasons, Module 4 (narrative exposure) needs to be delivered individually. Module 4 will take 5-7 sessions. Hence, due to budget constraints, only 5–10 participants will be chosen to complete the narrative exposure therapy component. We will ask participants if they are interested to conduct additional 4 sessions to enhance PTSD symptoms. We will ask one group at a time until the desired number is fulfilled.

It is expected that individuals who do not undergo the narrative exposure therapy module will still experience positive outcomes from the remaining components of the intervention, including improvements in symptoms of complex PTSD and overall functioning.

Participants will be divided into four groups. Each group will consist of five participants. Groups will be organized based on geographical preference of therapy and/or participant characteristics (e.g. gender or education level) to enhance group harmony and cohesiveness. Two psychotherapists, the applicant (who is a trained psychotherapist herself), and another psychotherapist, will be trained on using the manual and will lead group sessions. They will be assisted by two master-level psychotherapists in training. The graduate program committee in the counselling psychology program AUC agreed that two master's students could serve as co-facilitators as a part of their clinical internship.

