Supervision: During the 18-week intervention, weekly preparatory and peer-supervision meetings will be held. In-training therapists will have weekly supervision with [name] from AUC faculty. The whole team will also receive supervision from an experienced psychiatrist and psychotherapist with over 10 years of clinical and supervision expertise in third-wave cognitive-behavioral therapy modalities in group and individual formats (twice a month). This supervision model and team triangulation method ensure the quality and appropriateness of the intervention, as well as the ethical conduct of the students throughout their participation.

Following each therapeutic module, participants will complete an assessment including all outcome measures (see Section 3.10). Assessments will be conducted by either therapists or co-facilitators. Participants will also participate in a short qualitative interview in group format to provide their feedback on each module of the manual. Feedback interviews will be conducted by graduate (master-level) RAs. Initial baseline assessments will be administered by NH, who possesses a Citi training certificate, during the months of July and August. The T1, T2, and T3 assessments, which will be carried out by an RA(s), will not commence until September 21st 2025. Recruitment of the RAs has not yet taken place; however, it is scheduled to occur within the next month. After the recruitment of the RA, they will complete the Citi training and subsequently provide their certificate to the IRB prior to commencing any assessment activities. Please see Appendix 8 for sample patient feedback interview guide for module 1 & 2; provided are guides in English, once finalized guides will be translated in Arabic. Feedback focus groups will be audio recorded. For each assessment and feedback session participants will receive 700 EGP as compensation.

Therapists and co-facilitators will fill out a fidelity check form after each session, to retain information regarding the implementation, process evaluation, and acceptability of the intervention. Please see Appendix 4 for the fidelity form. Based on these forms, RAs will then conduct debriefing focus group discussions with therapists and co-facilitators after each module. Feedback from patients and therapists, will be used to make final adaptations in the adapted ESTAIR manual.

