Therapists and RAs costs are covered by the Prix CADOT funding. MA-level therapists in training cannot be paid as their work will count towards the hours they need to fulfill in their degree.

We provide below two tables with the weekly progression plans of the pilot study:

3 module plan:

Week	0	1	2-6	6	7-12	12	13-17	18	19
Visit	Study information & pre-assessment	Introduction session	Module 1	Intermediate assessment 1/Feedback	Module 2	Intermediate assessment 2/Feedback	Module 3	Final Session	Post-assessment/Feedback

4 module plan:

Week	0	1	2-6	6	7-12	12	13-17	17	18-24	25	26
Visit	Study information & pre-assessment	Introductory session	Module 1	Intermediate assessment 1/Feedback	Module 2	Intermediate assessment 2/Feedback	Module 3	Intermediate assessment 3/Feedback	Module 4 (individual therapy)	Final session	Post-assessment/Feedback

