3.11. Data Analysis

Statistical analysis plan

For primary outcomes: We will primarily assess feasibility by determining the percentage of participants who complete the study until the end (among those who sign the informed consent). Based on reported dropout rates from studies using similar modular interventions with trauma survivors, we will consider 80-90% participation and adherence as excellent, 70-80% as satisfactory, and 60-70% as acceptable [42, 77].

We will assess the ITI feasibility, using the same method based on the percentage of participants who complete the ITI; 80-90% participation and adherence is considered as excellent, 70-80% as satisfactory, and 60-70% as acceptable.

In addition, we will calculate the mean and standard deviation of completion rates to offer more detail into the variation in adherence.

For secondary outcomes: Descriptive statistics will be calculated for demographic information and baseline characteristics of participants. For clinical outcomes, we will analyze changes in PTSD symptomatology and other clinical outcomes (e.g., depression, anxiety, somatic symptoms, and well-being) at the four or five measurement points depending on group allocation. (See section 3.8 procedures). We will use intermediate assessments after each module to statistically describe the participants' state (means, standard deviations, correlations), enhancing our understanding of the effects of intervention components.

Next, we will use pre-post comparisons based on data from the first and last assessments to establish the status of change (clinically significant change) for each participant. We will conduct one-

sided paired measures Student's t-tests at the group level. The null hypothesis (H0) is that the change is zero. The alternative hypothesis (H1) is there will be a decrease in symptoms of CPTSD, depression, anxiety, and somatization; and an increase in rates of wellbeing. Student's t tests will be conducted with a significance level of 0.05. If the assumptions for the Student's t test are not satisfied, we will utilize non-parametric tests, specifically the Wilcoxon test for paired measurements.

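### Section 3.8 assigns the post-baseline questionnaires to two different sets of assessors, and the labels T1–T3 cannot cover all four follow-ups of the 4-module plan

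*Combined protocol and SAP*

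**What the plan says.** Section 3.8 (therapeutic program) states that participants complete all outcome measures after each module, and then: "Assessments will be conducted by either therapists or co-facilitators". The qualitative interviews have their own sentence: "Feedback interviews will be conducted by graduate (master-level) RAs". The applicant, who also leads groups, administers the baseline assessment. The text then continues: "The T1, T2, and T3 assessments, which will be carried out by an RA(s), will not commence until September 21st 2025". The RAs are not yet recruited, and they must "subsequently provide their certificate to the IRB prior to commencing any assessment activities".

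The two weekly plans in Section 3.8 place follow-ups at weeks 6, 12 and 19 (3 modules) and at weeks 6, 12, 17 and 26 (4 modules). The extra visit is "Intermediate assessment 3/Feedback" at week 17. The last visit in both plans is "Post-assessment/Feedback". Section 3.11 analyses outcomes "at the four or five measurement points depending on group allocation", and bases the one-sided paired tests on the first and last assessments. The labels T1, T2 and T3 appear only in the RA sentence and are defined nowhere.

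**The concern.** The protocol gives two incompatible rules for who collects the same questionnaires, so staff cannot tell from it who should be in the room at most follow-up visits.

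The statistical interest is narrow. The outcomes are self-reports, so no rater scoring is involved. A participant who hands the form to someone delivering the treatment may nevertheless report more improvement than to an uninvolved person. With no control arm, any such tendency at the last visit goes straight into the pre-post difference, in the direction that the one-sided tests look for.

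The label count adds to this. The RA sentence, taken alone, does not reach every follow-up, and under some numberings the visit it misses is the one that supplies the last value.

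**Working it through.** **1. Do the two sentences concern the same activity and different people?**
- Same activity: the T1–T3 sentence comes directly after the one on baseline assessments and continues that series. The feedback interviews are dealt with separately, so T1–T3 cannot easily be read as those interviews alone.
- Different people: Section 3.8 has RAs run debriefing groups with the therapists and co-facilitators. RA costs are funded, whereas the trainee therapists cannot be paid. The RAs are still to be recruited, whereas the use of two master's students as co-facilitators is already agreed.

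**2. Measurement points.** Counting visits in the weekly plans:
- 3-module plan: weeks 0, 6, 12, 19 = 4 points, so 4 − 1 = 3 follow-ups.
- 4-module plan: weeks 0, 6, 12, 17, 26 = 5 points, so 5 − 1 = 4 follow-ups.

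This reproduces the four or five points of Section 3.11. Three labels against four follow-ups leave 4 − 3 = 1 unlabelled visit per participant in the 4-module plan.

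**3. Number of visits.** Inputs: 20 participants (Section 3.6), 5–10 of them in Module 4 (Section 3.8), no dropout.
- 5 in Module 4: 15×3 + 5×4 = 65 follow-ups.
- 10 in Module 4: 10×3 + 10×4 = 70 follow-ups.

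The therapist sentence is taken to cover all of these, with the post-assessment counted as the one following the last module.

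**4. Visits claimed by both sentences.**

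| Meaning of T1–T3 | Claimed by both | Outside the RA sentence |
|---|---|---|
| First three follow-ups in visit order | 20×3 = 60; 60/65 = 92%, 60/70 = 86% | Week-26 post-assessment of 5–10 participants (25–50% of 20) |
| Numbered intermediate assessments 1–3 | 15×2 + 5×3 = 45 (45/65 = 69%) to 10×2 + 10×3 = 50 (50/70 = 71%) | Post-assessment of all 20 |

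A third possibility is that T3 means the post-assessment in both plans. The counts are then those of the first row, but the missed visit is week 17 and the last value is covered.

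**5. RA start date.** Section 10 starts group sessions in the week of 18 August. The year is taken as 2024, from the August 2024 recruitment deadline in Section 3.6 and the February 2025 end of the time plan. Week 6 is then 18 August + 5 weeks = 22 September 2024. The RA start of 21 September falls one day earlier if the year is 2024. This supports reading T1 as the week-6 assessment and 2025 as a slip.

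**The case against.** The best reply is that the text already shows which sentence is meant. The RA sentence comes later, names time points, gives a start date and ties the role to a training requirement. With the year corrected, its date matches week 6. Section 3.8 also describes supervision over an 18-week intervention, which is the 3-module plan, and there T1–T3 fit the three follow-ups exactly. The therapist sentence would then be a leftover, and the gap an unwritten T4 for the optional Module 4 extension.

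This is probably what was intended, and it tells us which sentence to keep. It does not remove the conflict: both sentences are in force, and the 4-module plan still has a follow-up that the RA sentence does not reach.

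The objection on bias also stands in part. The documents do not say that therapists would assess their own groups, and the questionnaires are completed on paper. The mechanism is plausible but not demonstrated. Moving to RAs also changes the assessor between baseline and follow-up, though the RA sentence already implies that change.

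**Conclusion.** The contradiction is real and unreconciled, and its consequence is minor. Both sentences claim 45–60 of the 65–70 planned follow-up visits, before dropout and with 5–10 participants in Module 4. The range reflects the undefined labels, so 86–92% should not be quoted as the overlap on its own.

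Four stronger readings are tempting, and the documents do not support them:
- **The pre-post results would be invalid.** The outcomes are secondary self-reports, Section 3.1 disclaims efficacy conclusions, and no document allows the size of a reporting bias to be estimated.
- **The RAs would arrive only after the study ends.** That takes the year 2025 literally. The match with week 6 of 2024 points to a slip, so the date needs correcting but does not measure the problem.
- **Therapists and co-facilitators would assess without training, or would read items aloud at follow-up.** Silence on their certificates does not show that they have none. Reading aloud is offered only at the screening session.
- **Assessor type would confound the comparison by number of sessions.** This would need both sentences to apply together. The contrast is exploratory and already compromised: entry to Module 4 depends on interest ("We will ask one group at a time until the desired number is fulfilled"), and its last visit is week 26 rather than week 19. Fixing the assessor would not make it interpretable.

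**What to change.** In Section 3.8:
- Delete the sentence that assigns assessments to therapists or co-facilitators. State instead that RAs who do not deliver treatment administer the self-report outcome questionnaires at every post-baseline visit, including the last one.
- Define T1–T3 as weeks 6, 12 and 19 for the 3-module plan, and T1–T4 as weeks 6, 12, 17 and 26 for the 4-module plan.
- Reconcile the RA start year with the time plan in Section 10.
- Reconcile the new wording with Section 4.2, which places an oral suicidality check in the intermediate assessments (45–50 visits by the count above). The check must stay explicitly assigned. Who performs it is not decided here.

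The cost is a wording change plus RA time. It adds 5–10 questionnaire administrations if RAs already do T1–T3 in visit order, 20 if they do only the numbered intermediate assessments (65 − 45 or 70 − 50), and up to 65–70 if they do none. RA costs are funded and RAs already run the feedback interviews, but their number and hours are not given. The report should note that the applicant administered baseline and RAs the follow-ups.

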3.9. Withdrawal & discontinuation

Participants can withdraw at any time during the interviews, without providing any reason. It is also expected in such trials that participants will drop out with giving notice.

In the event of an immediate threat of suicide or the presence of severe psychotic symptoms, participants will be removed from the study. Should these symptoms appear, the therapy will be suspended, and the participants will be guided by therapists towards appropriate services to facilitate the required clinical measures for recovery, such as crisis intervention, medication, and, if deemed necessary, hospitalization. See Section 4.2 in adverse events and see appendix 6 for emergency services list. In such cases the case of the participant will be discussed in team supervision meetings, which include a consultant psychiatrist, 2 clinical psychologists, and 3 counselling psychologists).

Data collected until that time point will be used, unless the participant requests destruction of his data.

Participants will be substituted if they drop out early (i.e. before the introductory group session before module 1 sessions begin).

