3.6. Target population

Our target population is Egyptian adults living in urban settings, i.e., major cities in Egypt. Egypt is a large, heavily populated, and diverse country, challenges encountered by urban populations may significantly differ from those faced in rural areas. Literature from LMIC show that urban environments are characterized by increased violence rates and limited healthcare resources [67]. As we aim to have our diagnostic module and therapeutic manual to be culturally and structurally sensitive, we thought that focusing on urban population will allow us to include more contextual variables thereby making the intervention more targeted and relevant.

The adapted manual will be piloted with 20 participants. We aim to recruit an equal number of male and female participants. However, this number may change since women seek help more than men in Egypt [68]. Given that the project is time-bound due to funding reasons and the progression of this PhD project, recruitment should be concluded by August 2024. This short time frame might limit our ability to make extra efforts to include additional male participants.

Patients are included if they are 18 years of age or older, can give written or oral consent, are literate, have a history of severe and/or prolonged trauma, and screen positive for CPTSD. The therapeutic program will take place in Cairo, however participants are allowed to join if they reside in any other major city, if they wish. They will be excluded if they present an imminent risk of suicide, psychotic symptoms, and/or severe alcohol and/or drug abuse, or have been in therapy before (i.e., completed more than 5-10 sessions of psychotherapy).

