3.12. Handling of missing data & dropouts

Given that this is an uncontrolled pilot study, its principal aim is to assess the feasibility and acceptability of the ESTAIR manual. We will therefore closely monitor dropout rates and conduct follow-up with individuals who withdraw from the intervention. During follow-ups we will also try to encourage participants to continue treatment. We will also conduct feedback interviews, when possible, with drop-outs, to understand reasons for dropout and have accurate representation of the feasibility and acceptability of our intervention.

Regarding statistical analyses, we will not be imputing missing data. Only participants who underwent assessment at both the pretest and post-test will be included in the analysis.

4. Ethical Considerations

Our participants are from a highly vulnerable population. This will require culturally sensitive and clinically trained professionals. To anticipate this, our research team consists of local experts, such as [name], who is highly experienced in trauma care clinical settings, as well as researchers. We also have [name], who has over 10 years of training professionals and experience working with vulnerable populations. We have connections to public and private hospitals in case of emergencies. All psychotherapists are also trained and have experience working with clients with severe mental health disorders and trained in this manual. [name], UniL Supervisor has connections with therapy developers in case any changes or accommodations to treatment is needed. This way we have local and international support of experts to ensure that we provide the best care for participants.

Other ethical considerations include the voluntary nature of participation in the project. Given the strain on public services in Egypt, the difficulty in accessing care, and the need for out-of-pocket payments, participation in our study may be the only affordable option for certain participants to receive

appropriate psychotherapeutic care. This may act as a strength in offering an additional option for care, but it may also be an ethical consideration. Our study offers them a standardized intervention that is based on and supported by evidence as an effective treatment for CPTSD, which is a better option than existing care options.

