4.1. Risk- benefit assessment and management

Our study's main benefit is that it may reduce psychological distress and improve functioning. ESTAIR is an evidence-based intervention. Our cultural adaptations have relied on evidence-based literature and fieldwork. Based on these facts, we assume that the ESTAIR intervention can reduce psychological distress symptoms.

The study entails only minimal risks for participants. The ESTAIR manual corresponds to the guidelines for treating PTSD. Yet, there is a risk that parts of the intervention will destabilize the participants during therapy. Evidence from face-to-face treatments suggests that between 5% and 10% of all patients experience a deterioration of their symptoms during treatment. However, this destabilization will be temporary, and overall, on the longer term, the program is considered beneficial, as evidence shows that culturally adapted trauma-focused interventions are effective [49] . Furthermore, the manual's first module, emotion regulation skills, aims to teach participants how to manage difficult emotions and stress. This will help them during the course of the intervention.

As in any clinical study, severe adverse events such as misuse of alcohol or drugs, self-harm, or suicidal ideation or attempts can occur during participation in the trial. The therapists will receive regular supervision from senior experts. They are trained for situations of crisis, such as severe emotional distress, dissociation, a temporal increase of suicidal thoughts, or other negative reactions to the treatment. Please refer to Section 4.2 for the protocol for adverse events and crisis situations.

Participants will receive therapy at no cost and will be compensated for all assessment and feedback interviews. Aside from attending the therapeutic program and assessments, no other commitments will be asked from them.

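### Section 3.9 ends study participation, not only therapy, after a serious safety event, so under 3.12 the person drops out of the secondary pre-post analysis: a low-priority, cheap improvement

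*Combined protocol and SAP*

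**What the plan says.** All references are to the combined protocol and SAP.

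- **3.9, Withdrawal & discontinuation:** "In the event of an immediate threat of suicide or the presence of severe psychotic symptoms, participants will be removed from the study". The next sentence begins "Should these symptoms appear, the therapy will be suspended", and the participant is then directed to crisis care, medication or hospital as needed. On data, the section says "Data collected until that time point will be used", unless the participant wants them destroyed. No return to the study and no later assessment is described.
- **3.12, Handling of missing data & dropouts:** missing values are not imputed, and "Only participants who underwent assessment at both the pretest and post-test will be included in the analysis". The same section plans follow-up of people who withdraw from the intervention, with feedback interviews where possible. It mentions no outcome questionnaires in that follow-up and does not name people removed for safety.
- **3.11, Data Analysis:** the first and last assessments feed two secondary analyses: a status of clinically significant change for each participant, and one-sided paired tests at 0.05. Primary feasibility is the share of consenting participants who finish the study.
- **3.6, Target population:** on entry criteria, "They will be excluded if they present an imminent risk of suicide, psychotic symptoms" (severe substance abuse and previous therapy are also listed).
- **4.1, Risk-benefit assessment:** "between 5% and 10% of all patients experience a deterioration of their symptoms during treatment".
- **4.2, Adverse Events:** covers recording, reporting and crisis handling. It does not provide for outcome scores after the event.

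**The concern.** Stopping treatment and leaving the study are different events, and 3.9 makes them one. Someone in acute suicidal crisis or severe psychosis clearly may need to stop group therapy. It does not follow that a later questionnaire should no longer be offered to that person.

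The consequence is selective missing data created by a protocol rule. Ordinary dropouts leave by their own choice; these people are taken out because they became seriously worse, even if they would later be willing to be assessed. Two secondary results could be affected. The mean pre-post change would omit them. So would the individual classification, where with about 20 people a single missing deterioration is visible.

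**Working it through.** The plan gives no removal rate and no calculation on this point, so there is no figure to reproduce. The check is a reading of the text followed by an illustration of scale.

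**1. The route through the text.** Post-assessment is at week 19 (three modules) or week 26 (four modules), according to the tables in 3.8. A person removed under 3.9 before then has data only up to removal, hence no post-test. Under 3.12 that person is outside the pre-post analysis, and nothing is imputed. Sections 3.12 and 4.2 describe contact or care after leaving, but no outcome measure. Scores from before removal may still enter the descriptive summaries after each module. Whether the 3.12 rule also governs the multilevel models in 3.11 is unclear; even if it does not, the scores stop at removal.

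**2. Shift in the mean change.** Inputs: 20 participants (3.6, 3.11); k = number removed (not in the documents, assumed 0 to 2); d = how much worse a removed person's eventual change would be than the completers' mean, in SDs of individual change scores (assumed; negative means better). In this step everyone not removed is taken to complete. If completers have mean m and removed people m − d, then

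all-starter mean = [(20 − k)m + k(m − d)] / 20 = m − kd/20,

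so the completer mean overstates improvement by kd/20.

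| | d = 1 | d = 0 | d = −1 |
|---|---|---|---|
| k = 0 | 0 | 0 | 0 |
| k = 1 | 0.05 | 0 | −0.05 |
| k = 2 | 0.10 | 0 | −0.10 |

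The right-hand column matters: a person who has had medication or hospital care by week 19 or 26 might score better than the completers' average, and then the omission understates improvement.

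**3. With fewer completers.** Section 3.11 grades completion between 60% and 90%, that is 12 to 18 of 20. Adding back one person with d = 1 moves the mean by 1/(n + 1): 1/19 = 0.053 SD at n = 18 and 1/13 = 0.077 SD at n = 12. At those rates 20 − 18 = 2 to 20 − 12 = 8 people are missing from the pre-post set for any reason. Safety removals are an unknown part of that number, possibly none.

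**4. Against sampling error.** With change-score SD = 1, the standard error of the mean is 1/√19 = 0.23 at n = 19 and 1/√12 = 0.29 at n = 12. One removal with d = 1 is therefore about a quarter of a standard error (0.05/0.23 = 0.22; 0.077/0.29 = 0.27).

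**5. Individual classification.** Suppose one person is removed after deteriorating, would still be classed as deteriorated at post-assessment, and nobody else deteriorates. The plan would report 0 of 19; with that person assessed, it would be 1 of 20, or 5%.

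**6. Power is not the issue.** Taking the 0.24 in 3.11 as a standardised paired change (its scale is not stated), one-sided power at 0.05 is 27.1% with 20 people, 26.2% with 19 and 25.2% with 18. One or two removals cost one to two points.

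**The case against.** The case for leaving the plan alone is substantial.

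- **The general cause is 3.12.** The requirement for both assessments excludes every non-completer, and safety removals are a small part of that group. This is correct. What is particular here is that the loss is imposed by the protocol and tied to worsening.
- **Removal protects the participant.** Someone in crisis should not face research demands, and self-report or consent may be unreliable in psychosis. This stands as a reason to stop therapy and delay assessment. It does not require that a later assessment never be offered.
- **Suspension may mean a pause.** Possibly, but removal from the study and the cut-off on data point the other way. If a pause is meant, 3.9 should say so.
- **Entry screening makes such events unlikely.** It does, and no removals at all is plausible.
- **Nothing rests on the result.** Section 3.1 rules out efficacy conclusions, and 3.11 admits low power. This is the main reason for low priority.

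Some stronger readings are tempting but not supported. A reader might infer that the results will certainly be tilted towards improvement; 3.9 sends these people to treatment that could improve their later scores, so the sign is open. A reader might take the 5% to 10% in 4.1 (1 to 2 of 20) as a removal rate; it describes deterioration in general, including milder worsening. And a reader might say the pilot fails to test the statement that "this destabilization will be temporary"; that is a background expectation in the risk-benefit section, which the pilot does not set out to test.

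**Conclusion.** The point holds in limited form. Section 3.9 takes these participants out of the study as well as therapy, and 3.12 then leaves anyone removed before post-assessment out of the secondary pre-post comparison and the clinically-significant-change classification. The loss is selective and may favour the intervention, but its direction is not certain.

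Its size cannot be derived from the documents. It is zero if nobody is removed, and within ±0.10 SD for up to two removals of 20 if d lies between −1 and 1; both the number removed and d are assumptions.

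Two things a reader might infer do not follow. The primary feasibility percentage is not biased, since removed participants stay in its denominator as non-completers. Nor are these participants abandoned: referral, call-back, supervision review and adverse event reporting are all provided for in 3.9 and 4.2. This is a low-priority improvement, worth making because it is cheap.

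**What to change.** In 3.9:

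1. State that these events stop or suspend therapy but do not end study participation unless the participant asks.
2. Offer the post-assessment already planned, when clinically appropriate and with continued consent.
3. Include those scores in the pre-post comparison, and report alongside them why therapy ended and what other care was received.
4. Keep counting these participants as therapy non-completers in the feasibility percentage.

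All existing protective steps remain as they are.

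Cost: one 700 EGP session per affected person, with no new staff, and an ethics amendment under 4.4. Some people will decline, and late scores will partly reflect other care, so only part of the lost information is recovered.
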